Objective 2: Evaluate the impact of a storytelling intervention on adherence to PrEP/ART medications.

Objective 3: Assess the experiences of participants and family members in the storytelling intervention.

6. Design and Study Questions

The proposed study is a two sample, couple-randomized pilot to test the impact of an oral storytelling intervention (versus standard of care PrEP/ART delivery) to increase retention in, and adherence to, PrEP and ART among HIV-discordant expectant couples.

There are seven specific study questions:

Question 1: Is our intervention idea acceptable to discordant expectant couples and their families?

Question 2: Does our intervention positively impact partner support for PrEP/ART medication adherence and retention in care?

Question 3: Does the intervention increase empathy among partners enrolled?

Question 4: Does the intervention increase knowledge about HIV?

Question 5: Does the intervention reduce depression among couples enrolled into the intervention?

Question 6: Does our intervention improve the proportion of exposed infants who are tested for HIV (early infant diagnosis [EID])?

Question 7: Does it decrease the number of infants who are HIV-positive at 12 months?

7. Study Population

a. Population:

1. Couples consisting of two adults 18 years or older (one HIV-uninfected pregnant woman and her HIV-infected male partner) presenting for ANC services together in Zambézia province, and their infants.
2. Family members of couples in the intervention group who participate in the storytelling events.

b. Inclusion Criteria:

1. Couples, one pregnant woman and her male partner, will be eligible to participate if: i) the male partner is identified as HIV-positive at any ANC appointment, either through ANC-based HIV testing or having a known history of HIV-positive (from clinical records or medication pick-up documents, or any other mechanism by which ANC staff identify him as HIV-positive); ii) both persons agree to take PrEP (pregnant woman)/ART (male partner) together and receive standard care in pre- and postnatal period, including care of the HIV-exposed infant (“CCR – Consulta de Criança em Risco”; iii) the woman’s due date is >4 weeks from study enrollment; iv) both persons are 18 years or older; v) both persons are able to give informed consent; vi) both persons (parents) are willing to consent to an infant record search, and v) both persons consent to be in the study.

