Objective 3: Qualitative interviews will be measured using open-ended interview questions to understand their perspectives and experiences with the study activities, strategies, benefits, disadvantages, and suggestions for program implementation and improvement. These qualitative interviews will not necessarily provide objective measurement, but rather in-depth information regarding program implementation issues and strategies for improvement.

b. Instruments used in the study

We will use the following instruments in the study: (1) depression;[79] (2) partner and family support;[60, 80] (3) empathy;[81] (4) relationship satisfaction;[82] (5) PrEP adherence knowledge; and (6) motivation/perceived ability to adhere to medication[83] at baseline and three months (Appendix 3). These instruments are quantitative scales with closed ended response options. During qualitative interviews with our smaller samples we will follow semi-structured interview guides (Appendix 4).

c. Anticipated end date of study:

This study is expected to be concluded in September 2020.

9. Locations of Study

This pilot will be conducted at Namacurra Sede health facility.

10. Data Management and Analysis

Data Management and Security

The data collected will be kept in a database housed in Mozambique. Data will be stored in a restricted access folder that sits on the FGH server. In addition, data will be password-protected to limit access to staff involved in the study and to ensure confidentiality. Data will be encrypted,

backed up on FGH servers, and uploaded to the VUMC servers as needed for PI access. FGH servers have daily backups scheduled; therefore, all data will be backed up on a day-to-day basis.

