Audio files will be transcribed verbatim by a research assistant and two researchers will code and analyze the interviews using MAXQDA® software. We will employ a thematic approach to identify and analyze themes in the data.[84] We will focus on two key reactions to the storytelling: (1) the experience of listening to the stories, with a focus on the effectiveness of the narrators ability to transport the listener, the level of identification and perceived similarity with characters; and (2) the impact of the storytelling intervention on information related to PrEP/ART adherence, motivation to adhere to medication due to self-efficacy, family support and feelings of depression/hopelessness, and behavioral skills learned. We will use a combination of deductive codes based on findings from previous adherence research and inductive codes to categorize newly-identified factors associated with uptake, adherence, and retention in PrEP/ART services (e.g. self-efficacy, partner support, information etc.). Two researchers will read through the transcripts several times and highlight relevant examples of storytelling impact on information, behavioral skills and motivation. Researchers will generate codes and highlight themes by collating codes across the data set and the review themes to develop a thematic map (e.g. the influence of a character's successful use of a strategy on a listener's self-efficacy to employ the same tactic). The final coding framework will have at least 85% agreement between the two coders. This exercise will allow us to modify our behavioral model if necessary.

Quantitative Analyses

AIM 1 Endpoints: (1) partner/family support;[60, 80] (2) empathy;[81] (3) relationship satisfaction;[82] (4) PrEP adherence knowledge; (5) depression[85]; and (6) motivation/perceived ability to adhere to medication[83]

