Secondary analyses will also follow intent-to-treat protocol, again operationalizing the outcomes in the negative (monthly count of missed doses; monthly nonadherence) such that the rate or risk ratios will be <1.0 if the intervention is effective. We will estimate the intervention effect on the count of monthly missed doses using a negative binomial regression model to account for overdispersion due to an excessive amount of zero missed doses (perfect adherence). In addition to clustering of couples, each participant will have up to three observations (one for each month of follow-up). Participants LTFU will only contribute an observation for each completed month of follow-up for which there is a pill count, otherwise they are censored. Similarly, self-reported monthly nonadherence is likely to be heavily skewed with a large proportion of 0% nonadherence. As this is inherently a continuous measure (rather than a count), we will dichotomize as 0% nonadherence vs. $>0\%$ nonadherence and each participant will contribute an observation for each completed month of follow-up. A sensitivity analysis will be performed with dichotomization at $\leq 10\%$ nonadherence vs. $>10\%$ nonadherence. As for the prior analyses, we will utilize GEE models (accounting for clustering of couples and repeated measures on individuals) with an interaction term between intervention arm and gender and will explore modification and adjustment for other covariates as described in Aim 1.

Objective 3: Following completed interviews, audio files will be transcribed by the interviewer, and the PI will code and analyze the interviews using MAXQDA 12® software. Framework Analysis will be used to identify responses to questions about the drivers, core facilitators, and barriers to intervention acceptability and success using grounded theory.[86] Two code maps will be developed to categorize data: (1) to understand the social, structural, and informational drivers, facilitators, barriers to recruiting, providing services for, and supporting discordant couples in

couple-based ANC and post-natal care; and (2) to understand concepts of “best-practice” for scaling up and implementing these services, particularly in regards to family engagement and using stories for educational purposes.

11. Ethical Considerations

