Appendix 4: Semi-structured interview guide for intervention couples and their families

Note: For use in completing in-depth interviews with couples and with their families.

Intervention Couple questions

1. Tell me what were the common messages you heard in the PrEP stories? Did they sound like issues that might be common here in Zambézia?
2. Did you think the stories addressed the major concerns people have with PrEP during pregnancy here in Mozambique? What did they miss?
3. What were your favorite parts of the stories? What parts did you like the least?
4. How have the stories impacted your motivation to take your medication? (what is the most important reason you take your medications? If you don't take them, why are you not motivated?)
5. How did the story impact your belief in your ability to take the medication every day? (what strategies did you learn that help you remember to take your medications?)
6. If you take your medications regularly, do you believe you can remain HIV-uninfected?
7. Did the stories change your partners view about taking medications?
8. Did the stories change your family's attitudes towards discordant couples staying together? Did the stories change your family's view of PrEP/ART use?

Intervention Family questions

1. Tell me what were the messages you heard in the PrEP stories? Did they sound like issues that might be common here in Zambézia?
2. Did you think the stories addressed the major concerns people have with PrEP during pregnancy here in Mozambique? What did they miss?
3. What were your favorite parts of the stories? What parts did you like the least?
4. Do you think that an HIV-negative pregnant woman should stay with an HIV-positive man? Should she continue to have sex with him?
5. Did the stories change your view of PrEP?
6. Did the stories change your view of discordant couples?
7. How did hearing the stories help you provide support to your family? (things to say, ways to help?)
8. Do you believe that PrEP can prevent a pregnant woman from contracting HIV? What are some reasons it might not work?
9. If you were making up your own stories to help discordant couples and their families, what are other topics you would add? What else would be helpful to know?

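### Parts of the Objective 3 code maps (recruitment, service provision, scale-up) have no matching interview questions or informants, and the two qualitative analysis plans conflict on coders and method

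*Combined protocol and SAP*

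**What the plan says.** Section 5 defines Objective 3 as: "Assess the experiences of participants and family members in the storytelling intervention". Study question 1 in section 6 is: "Is our intervention idea acceptable to discordant expectant couples and their families".

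Section 8a (Measurement of Results, Objective 3) says the interviews will yield views on study activities, including "benefits, disadvantages, and suggestions for program implementation and improvement".

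Section 10 (Data Analysis, Objective 3) plans two code maps. One covers drivers, facilitators and "barriers to recruiting, providing services for, and supporting discordant couples" in antenatal and post-natal care. The other covers best practice "for scaling up and implementing these services, particularly in regards to family engagement and using stories for educational purposes". The same paragraph states that "the PI will code and analyze the interviews using MAXQDA 12® software", and it names Framework Analysis with grounded theory.

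Section 10 (Qualitative Analyses) gives coding to two researchers using a thematic approach, and adds: "The final coding framework will have at least 85% agreement between the two coders". The data management text of section 10 also assigns coding to two people, one of them a study assistant.

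Appendix 4 holds the interview guide, with 8 questions for couples and 9 for family members. Family question 7 begins: "How did hearing the stories help you provide support to your family".

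**The concern.** A code map can be filled only if respondents are asked about its topics or are placed to know about them. Where neither holds, the codes rest on incidental remarks. Section 8a says each interview is done once with no follow-up, so a gap cannot be closed later.

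The interviews are also the main direct evidence on study question 1, because the scales in Appendix 3 include no acceptability measure. If the guide asks about the stories but not about the sessions, drawbacks such as having relatives present or hosting the session at home may go unrecorded.

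Finally, section 16 states that the PI took part in designing the interviews and producing the intervention. A plan that can be read as allowing the PI to code alone leaves interpretation open to an avoidable bias. Section 12 says the pilot is meant to show signals that support a larger trial, so these findings would feed into its design.

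**Working it through.** No arithmetic beyond counting applies. The check sets the guide beside the code maps, and then the analysis statements beside each other.

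**Step 1. Guide against code maps.** Appendix 4 has 8 + 9 = 17 questions.

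| Element of the code maps | Guide questions that address it | Count |
|---|---|---|
| Map 1: recruiting couples | none | 0 |
| Map 1: providing services in antenatal and post-natal care | none | 0 |
| Map 1: supporting couples | couple 7 and 8, family 7 | 3 |
| Map 2: scale-up as such | none | 0 |
| Map 2: family engagement | the same three support questions, in part | (3) |
| Map 2: use of stories | couple 2 and 3, family 2, 3 and 9 | 5 |

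The remaining 17 − 3 − 5 = 9 questions cover messages heard (couple 1, family 1), motivation and self-belief (couple 4 and 5), belief that PrEP works (couple 6, family 8) and attitudes to PrEP or discordant couples (family 4, 5 and 6). They bear on the stated objective but not on recruitment, service delivery or scale-up.

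**Step 2. Informants.** Section 7d plans interviews with 25 to 40 family members and 15 to 20 couples, all of whom took part in at least one session. Counting one interview per couple, that is 25 + 15 = 40 to 40 + 20 = 60 interviews. None is with a provider or with a couple that declined, so the people best placed to describe barriers to recruitment or service delivery are not interviewed.

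**Step 3. Disadvantages.** Four questions openly invite criticism: couple 2 and family 2 (what the stories missed), and couple 3 and family 3 (parts liked least). All four concern story content. None concerns the sessions: their setting, relatives being present, or why one was missed. Family question 7 asks how the stories helped, which takes for granted that they did.

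**Step 4. Analysis statements in section 10.**

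| Feature | Objective 3 paragraph | Elsewhere in section 10 |
|---|---|---|
| Coder | the PI | two people (data management text and Qualitative Analyses) |
| Method | Framework Analysis, grounded theory | thematic analysis (Qualitative Analyses) |
| Agreement target | none stated | at least 85% (Qualitative Analyses) |
| Transcriber | the interviewer | field workers (data management text); a research assistant (Qualitative Analyses) |

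The transcriber labels may describe the same staff. The coder and method entries cannot be read as one plan. The Qualitative Analyses text follows an Objective 1 heading, so it could in principle concern different data. But the documents describe only one set of interviews, and that text analyses reactions to the storytelling, so both plans appear to apply to the same transcripts.

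**The case against.** The strongest reply is that most of Objective 3 is well served. The objective is experience of the storytelling, and the guide asks about messages, local relevance, likes and dislikes, motivation, changed views and family support. The sentence that introduces the code maps also aims at acceptability and success of the intervention. This stands. A reader might infer from the gaps that Objective 3 cannot be answered or that the code maps have no source data at all. The documents do not support that: three questions feed the supporting element of map 1 and five feed the story element of map 2.

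The guide is also semi-structured, so interviewers may probe. That helps only in part, because the guide gives no prompt for the missing topics and the informants do not change.

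Recruitment barriers have another source: reasons for refusal are collected under section 8a and Appendix 1 (item 3). This stands too, but those are study records and not the interview responses that the Objective 3 paragraph would code.

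A reader might also infer that the guide as a whole is slanted toward success. Most effect questions are open in direction, family question 7 is the clear exception, and section 8a selects roughly equal numbers of adherent and non-adherent participants. Nor do the documents establish that the PI will code alone, since two other places plan two coders. The 85% target is attached to the two-coder plan and is not itself inconsistent. The fault is that the plans have not been reconciled.

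**Conclusion.** The point holds as a minor one. The recruitment, service-provision and scale-up elements of the two code maps have no question among the 17 in the guide, and no provider or refuser is interviewed. Disadvantages are probed through story content only, and family question 7 presumes benefit. The Objective 3 paragraph conflicts with the rest of section 10 on coders and method.

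Objective 3 can still largely be answered, and the randomised comparisons are unaffected.

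This rests on two assumptions: that Appendix 4 as shown is the complete guide, and that the two analysis descriptions refer to the single set of interviews that the protocol describes.

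**What to change.** 1. State one qualitative analysis plan in section 10, with one method and one description of who transcribes. Use the two coders already planned, at least one of them not the PI, and keep the 85% agreement target.
2. Cut the code maps to what the guide and informants can support: experience of the sessions, partner and family support, and use of stories. Report recruitment barriers from the refusal reasons that are collected separately.
3. Add a few neutral questions to Appendix 4: what was difficult or unwelcome about the sessions, what it was like to have relatives present, why any session was missed, and what could make delivery hard elsewhere.
4. Reword family question 7 so that it asks whether, and in what way, hearing the stories affected the support given.

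The cost is revised wording in section 10 and Appendix 4 and a few more minutes per interview. No coders are needed beyond those already planned.

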Family-based support systems are essential to changing health-related behaviors. Families, including couples, are a proven, effective unit of intervention in the African HIV prevention and care context. [29, 34, 36, 37, 39, 44-52] Our successful "Men for Health" program was designed to increase male participation in ANC services, including couple-based HIV testing. We trained "male champions" to counsel husbands about the importance of ANC uptake, HIV counseling and testing, and the need for men to provide physical and emotional support to their partners during pregnancy. Male partners were encouraged to accompany their wives to the health facility for ANC services. Traditional Birth Attendants (TBAs) were trained to provide similar education to pregnant women. We increased couples testing from 2% to 60% in less than three years.[44] While couple-centered behavioral interventions have been effective in reducing sexual and drug-risk behaviors, increasing access to HIV testing, and improving uptake of PrEP services,[29, 34, 36, 37, 39, 44-56] no studies have assessed the effect of family-centered interventions on adherence to maternal PrEP/paternal ART during pregnancy and lactation.[14]

Will treatment adherence by one partner result in decreased adherence by the other?
Will serodiscordant partners receive differing levels of family support (i.e. more support for negative woman or positive man)?
Do people learn more about PrEP via storytelling vs. counseling sessions?
Can family support for PrEP use overcome partner neglect or rejection? Or Can partner support for PrEP use overcome extended family neglect/rejection?

Table 2: Unique social challenges faced by serodiscordant couples

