2. Family members (as defined by relatives living in the participants’ household or relatives the participants identify as living in the study community) will be eligible to participate if: i) they participated in at least one of the storytelling sessions; ii) are 18 years of age or older; iii) are able to give informed consent; and iv) are willing to participate in the interview.

c. Exclusion Criteria:

1. Couples will not be eligible to participate in the study if the woman is not pregnant, if she is HIV-positive or if her partner is not HIV-positive, if either person is younger than 18 years, if one member of the couple is unwilling to enroll in PrEP/ART or consent to the infant record search, or if one member of the couple is unable or unwilling to give informed consent for any reason.
2. Family members will not be eligible to participate in the study if they do not participate in at least one storytelling session, if they are younger than 18 years old, if they are unable or unwilling to give informed consent for any reason (e.g. have been drinking or show other signs of mental limitations), or if they are not willing to participate in the interview.

d. Calculations of Sample Size:

Objectives 1 & 2: Our pilot will involve 70 couples (70 HIV-negative pregnant women and their HIV-positive male partners; 35 couples in each arm) from a single clinic. Limited data on PrEP in Mozambique suggest 55% of pregnant women were not retained at 3 months after PrEP initiation. Given our sample size of 70 women and a 5% type I error, we will have 82% power to detect a RR of 0.40 for not being retained. Should there be evidence the intervention effect is similar for men and women with regards to retention, the two groups can be analyzed together to further improve power to detect RRs closer to 0.50. We do not have estimates of Tenofovir levels among PrEP users, but other studies indicate as many as 70% may have no active drug detected.[76]

Given our sample of 70 women and a 5% type I error, we will have 85% power to detect a RR of 0.50 for no detectable drug level.

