Family members of intervention participants who are nominated for participation by the discordant couple will be recruited by the study assistant at the home of the discordant couple (already consented and enrolled in the study). The discordant couple will ask their family member(s) to stay home or invite their family member(s) over during a pre-arranged time slot, and the study assistant will meet them there to explain their potential participation in the trial and to obtain the family members' consent (if applicable).

g. Patient participant retention and withdrawal:

Participant retention and withdrawal from clinical care: As per standard clinic procedure, peer educators will track all patients who miss appointments at the health facility selected as study site. The peers will document patients as terminating clinical care services if they: (1) discontinued

services due to death; (2) transferred their care to another clinic; (3) are lost to follow-up (defined as being >60 days late for a clinic appointment); or (4) discontinue for any other reason, including patient choice.

[figure not shown]
Participant retention and withdrawal from pilot: Study participants can choose to discontinue participation in the study and decide that their medical data and/or study data cannot be used in the analysis at any time by formally communicating their decision to the study manager.

8. Methods

a. Study Procedures for patients

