A participant's study information will not be released without the written permission of the participant. All study-related information will be stored securely at the study site. All participant information will be stored in locked file cabinets in locked rooms, i.e., access is limited to study staff. All study data collection, process, and administrative forms and other reports will be identified by a coded number to maintain participant confidentiality. All records that contain names or other personal identifiers, such as locator or informed consent forms, will be stored separately from study records identified by a code number. All databases will be secured with password-protected access systems. Forms, lists, logbooks, appointment books, and any other listings that

link participant ID numbers to other identifying information will be stored in a separate, locked file in an area with limited access.

Consent Procedures

The consent procedures are detailed above and the consent forms can be found in the Appendix (Appendices 5, 6, and 7). The signed consent forms will be kept in a lock box at the FGH office in Quelimane, separate from the transcripts of the interviews. The consent forms will be kept for seven years, at which point they will be burned to ensure that no one will be able to link any consents to participants.

Evaluation of benefits and risks

Adverse events

Risks to the subjects (both intervention and control group and family members): The level of risk associated with this research is expected to be minimal for all participants. Potential psychological discomfort may occur when administering the survey for participating couples, as many of the questions are personal and have to do with a stigmatized infectious disease. All participants are able to decline to answer any question that they deem uncomfortable.

Adverse Experience: We do not anticipate any adverse events as a result of this study, however study participants will be provided with a telephone number and instructed to contact study clinicians to report any serious AEs they experience.

Protection against risks: The study protocol and training manuals will include strict guidelines for conducting the survey and recording the data in a confidential manner. All study staff will receive formal responsible conduct of research training per NIH, VUMC, and Mozambican Ministry of Health guidelines. Participants may withdraw from the study for any reason at any time.

Benefits

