Appendix 2: Storytelling Intervention

The three motivational stories include the following themes:

- (1) A couple who has to overcome the difficulties associated with having a different HIV status compared to their partner. Specifically, how they address accusations of infidelity, how they manage to take different medications, interpret different messages (lifelong ART vs. short term PrEP), and a woman's concerns with seroconversion. How their family provides emotional and physical support via assistance in food preparation, completing chores around the house, and counseling both partners not to give up on the medication.
- (2) A woman who overcomes the difficulties of an unsupportive husband and extended family. The story of a woman who wants to take PrEP but must take medication and attend clinical visits without detection. The challenges she encounters while hiding her treatment, the moment of discovery, and how she successfully changes the beliefs and attitudes of her husband and extended family.
- (3) An encouraging couple who overcomes the difficulties of an unsupportive extended family. The story of a couple who support each other in medication adherence but face the scorn and derision of their extended family. The extended family blames the man for exposing the pregnant woman and her unborn child to HIV. The strategies this couple uses to change the attitudes and options of their family, to remain adherent to medication, and to have an HIV-uninfected baby.

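### Section 11 names only survey discomfort as a risk, and no data item records disclosure, blame, separation or violence linked to the family sessions; harm by arm could be seen only indirectly

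*Combined protocol and SAP*

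**What the plan says.** The design is a "two sample, couple-randomized pilot to test the impact of an oral storytelling intervention" (section 6), with 35 couples per arm at one clinic (section 7d).

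On risk, section 11 rates the level as minimal for couples and relatives alike. The one risk it names is this: "Potential psychological discomfort may occur when administering the survey for participating couples". It then states "We do not anticipate any adverse events as a result of this study". The same sentence goes on to give participants a telephone number for reporting serious adverse events. The text does not define serious, and section 10 has no analysis of adverse events.

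On contact with relatives, section 7f says the couple nominates relatives and arranges for them to be at home, where "the study assistant will meet them there to explain their potential participation in the trial". Section 8a then describes three storytelling sessions, each followed by a facilitated discussion, with relatives of the couple's choosing, at home or another place they prefer.

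On family conflict, Table 2 asks "Can family support for PrEP use overcome partner neglect or rejection". The background says discordant couples are less likely to stay together than concordant ones. Appendix 2 includes accusations of infidelity in story 1 and, in story 3, "The extended family blames the man for exposing the pregnant woman and her unborn child to HIV".

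On measurement, depression, partner and family support, and relationship satisfaction are collected from both partners at baseline and three months (sections 8a and 8b, Appendix 3) and compared by arm (section 10). Appendix 1 takes marital status at enrolment only.

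**The concern.** The risk statement covers the questionnaire and says nothing about the intervention. Every enrolled man is HIV-positive with an HIV-negative pregnant partner, so an honest explanation of the trial to a relative can reveal his status. The visible text has no step that confirms which nominated relatives already know. The background reports that more than 95% of patients have told at least one relative, but that is not the same as having told each person invited.

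If a session led to blame, separation or a threat, the only formal route is for the participant to judge the event serious and telephone. The pilot is meant to detect signals of success and support funding of a larger trial (section 12). It could report better support scores without being able to say how often, in either arm, these specific events occurred.

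**Working it through.** **Step 1. Recognised hazards set against data items.** The visible protocol body and Appendices 1, 3 and 4 give:

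- *Unwanted disclosure:* no item in Appendix 1 or 3, and no interview question on it.
- *Blame or rejection by relatives:* recognised in Table 2 and Appendix 2. There is no event item. The Berlin Social Support Scales measure perceived support from people in general.
- *Separation:* recognised in the background. Marital status is recorded only at enrolment, and monthly status distinguishes active, default, lost, transferred and dead.
- *Threats or violence:* no item. The visible text does not mention violence; including it is the review's inference.
- *Loss of support:* already covered by the Berlin scales in both arms.
- *Distress:* covered by the PHQ-9 (including its self-harm item) and the relationship-satisfaction scale, in both arms.

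**Step 2. The plan's own figures.** No figure for harm is stated. The stated power confirms 35 per arm as the basis. The formula is power = Φ[(d − 1.96·√(2p̄(1−p̄)/n)) / √((p1(1−p1)+p2(1−p2))/n)], with n = 35, two-sided 5% and no dropout:

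- Not retained, 0.55 vs 0.22: (0.33 − 0.228)/0.1094 = 0.932, power 82.4% (stated 82%).
- No detectable drug, 0.70 vs 0.35: (0.35 − 0.234)/0.1118 = 1.038, power 85.0% (stated 85%).

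**Step 3. What a direct item could show.** These figures assume all 35 couples in an arm are asked and answer fully.

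- Upper 95% limit for 0/35: one-sided 1 − 0.05^(1/35) = 8.2%; two-sided 1 − 0.025^(1/35) = 10.0%.
- Chance of at least one event in an arm, 1 − (1 − p)^35. The documents give no rate, so p is assumed: 2% gives 51%, 5% gives 83%, 10% gives 97%.

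**Step 4. What passive reporting loses.** Suppose a fraction s of events is telephoned in (an assumption). At a true rate of 5%, 1 − (1 − 0.05s)^35 is 16% for s = 0.1, 41% for s = 0.3 and 59% for s = 0.5, against 83% with full ascertainment.

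**Step 5. Limits of a comparison.** With the Step 2 formula, power is 12% for 5% vs 10% and 21% for 10% vs 20%. Against a 5% control rate, 80% power needs about 31% in the other arm. For the existing scales within one gender, 80% power needs a standardised difference of (1.96 + 0.84)·√(2/35) = 0.67.

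**Step 6. Incomplete follow-up.** As an illustration, if survey completion fell as low as the 45% retention implied by section 7d, about 16 of 35 couples would answer (0.45 × 35 = 15.75). At a true 5% the chance of seeing an event would be 1 − 0.95^16 = 56%. The upper one-sided limit for 0/16 would be 1 − 0.05^(1/16) = 17%.

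**The case against.** The strongest reply is that the plan is far from blind to harm. Depression, relationship satisfaction and support are measured in both partners and both arms. The Aim 1 models estimate an arm effect with a gender interaction, which would show worsening as readily as benefit. The relationship scale asks how many problems there are and how often the respondent regrets the relationship. Interviews seek disadvantages and deliberately include non-adherent participants. Peer educators trace missed visits and separate death, transfer, loss to follow-up and other reasons, among them the patient's own choice (section 7g). The couple chooses the relatives and the place, issues the invitation, and is told before consent that relatives will take part. Study information is not released without written permission.

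Most of this stands. A reader might infer that harm by arm cannot be seen at all, or that there is no measurement of social harm. The documents do not support that, because the scales compared by arm would show a general deterioration. A reader might also infer that every couple lost after a bad session would pass as routine loss to follow-up. Section 7g provides for recording departure by choice, though not necessarily its cause.

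The reply does not cover specific events. Mean scores at one time point do not identify or count them, and couples who have separated may be missing from that survey. The interviews have no control group. Choosing the relatives lowers the disclosure risk, but nothing visible checks it.

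Table 2 poses a research question, story 3 uses blame as an obstacle to overcome, and discordance is present in both arms. These passages show that the protocol recognises the hazards; they do not show that the sessions cause them.

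**Conclusion.** The point holds as a gap in the risk statement and in event capture. It is an inexpensive improvement and does not invalidate the efficacy analyses. Section 11 names no risk from the intervention, its only adverse-event route is self-reported and limited to serious events, and four specific social harms have no data item. Indirect evidence by arm exists through the scales.

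The conclusion is limited to the visible protocol body. Consent Appendices 5 to 7 are not available and the training manuals are not included, so wider risk wording or a disclosure check may exist there. The documents therefore do not support a claim that participants are not warned.

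The event rates and reporting fractions used above are assumptions, and the detection probabilities need full ascertainment. At 35 couples per arm, direct items would give counts and wide intervals and no useful test. Zero events would not establish safety, since rates up to about 8% (one-sided) or 10% (two-sided) would remain compatible with the data.

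**What to change.** 1. Add three or four yes/no items to the existing 3-month survey: unwanted disclosure of HIV status, blame or rejection by relatives, separation from the partner, and threats or violence. Ask each partner privately, in both arms. A separate loss-of-support item is unnecessary because the Berlin scales cover it.
2. In section 10, state that counts with exact 95% intervals will be reported by arm as descriptive only. Use the couple as the unit (either partner reporting), or report women and men separately, so that two partners are not counted as independent. Give the number who answered in each arm, because couples who separate may be the ones missing.
3. Before the first family contact in section 7f, have the couple confirm which nominated relatives already know the man's status, and limit what staff say accordingly.
4. Amend the section 11 risk statement to name these intervention risks, and check that the consent forms agree with it.

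The cost is a few minutes per participant, one checklist line and some protocol wording, with no added visit or sample. Asking about violence also means the investigators and ethics committees must agree beforehand how a positive answer is handled. The downside is that the items give no power for a formal comparison between arms.
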